# 7.6 Sub-gingival Plaque Samples

Sub-gingival plaque will be collected using sterile paper points inserted in the gingival sulcus for 30 seconds from the mesiobuccal and mesiopalatal surfaces of teeth numbers 14, 15, 16, 24, 25, and 26). Plaque samples will be placed in microcentrifuge tubes then transported on ice to -80°C freezer in our lab at Dental Sciences building, at University of Toronto, Faculty of Dentistry. There they will be processed and analyzed by shotgun metagenomics and targeted proteomics.

#### 7.7 Saliva and Oral Rinse Samples

Saliva samples (5 ml) will be collected at all visits and placed on ice to -80°C freezer. Samples will be sent our lab at Dental Sciences building, at University of Toronto, Faculty of Dentistry. There the saliva samples will be processed and undergo 16S rRNA sequencing and targeted proteomics analyses. The oral rinse samples will undergo oral neutrophil count.

# 7.8 Halitosis Measurement

The Halimeter PLUS is a specialized instrument designed and manufactured by Interscan Corporation to measure the concentration of volatile sulfur compounds (VSC), particularly hydrogen sulfide, methyl mercaptan, and dimethyl sulfide, in a person's breath. These compounds are often associated with oral malodor, commonly known as bad breath. The Halimeter contains electrochemical sensors that detects the concentration of VSCs in breath. When a person exhales into the device, the sensor measures the levels of these sulfur compounds, providing a quantifiable reading. Elevated levels of VSCs indicate the presence of oral bacteria and potential oral health issues.

Since all research projects will be done on de-identified samples, it will not be possible to return individual results to participants. Unless participants ask to withdraw from the study, samples may be retained indefinitely. Because all research will be done on de-identified, aggregated data, it will not be possible to withdraw the data from a specific participant when samples are withdrawn from the study.

# 8.0 STATISICAL ANALYSES

Correlations between tissue and blood neutrophil subsets and standard periodontal disease parameters from oral exam will be assessed. Data will be complied in SPSS version 20. Changes in the clinical parameters of experimental gingivitis such as bleeding on probing, gingival index, plaque index and probing depths during day 0, 7, 14, 21, 28 and 35 will be compared using one-way analysis of variance (ANOVA) followed by Tukey multiple comparison.

Oral neutrophil counts as well as neutrophil subset formation during day 0, 7, 14, 21, 28 and 35 in oral rinse samples as well as blood samples will be compared using one-way analysis of variance (ANOVA) followed by Tukey multiple comparison.

Multiple sites within each study participant will be evaluated using a Gingival Bleeding Index (BOP) at baseline and 3-week post product use exams. The gingivitis bleeding scores will be averaged to provide a mean score per study participant for each exam period. Product means and standard deviations will be calculated for each time period. Analysis of Variance techniques (possibly including Analysis of Covariance using the baseline scores as the covariant) will be used to compare the difference between the two test treatments using the 95% confidence level ( $p \le 0.05$ ). The correlation of baseline to post-treatment results will be assessed graphically. If there is evidence of correlation, the baseline result will be included in the ANOVA model to adjust for baseline differences.

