# 6.5 Pre-Induction Phase (Health Baseline – Study participant maintain dental hygiene at home for 14 days)

# 6.5.1 Visit 1 (t-2) Day -14

Study participants will undergo an oral hard and soft tissue exam as well as measurements of probing depth (PD), attachment level (AL), visible plaque index (VPI), gingival index (GI) and bleeding on probing (BOP) and recorded on the Oral Assessment Form (Appendix 7). The biospecimens collection will include gingival crevicular fluid (GCF), sub-gingival plaque, saliva and a saline oral rinse. All study participants will receive a prophylaxis (cleaning) which involves scaling and polishing to remove all supra- and subgingival plaque and calculus. Study participants will receive their assigned study product for use at home with directions. The participants will take two lozenges daily, one after their morning brushing and one after evening brushing. They will allow the lozenges to dissolve without biting or swallowing and avoid eating and drinking for one hour. The participants will be instructed on proper oral hygiene and will be instructed to continue their home oral hygiene in addition to use of their assigned product for 14 days (2 weeks). The participants will be instructed to return the lozenges' containers at each visit for protocol compliance check. Researchers will query participants on their use of NHPs, as well as any adverse effects they experienced.

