# 6.6 Induction Phase (No Oral Hygiene – for 21 days)

# 6.6.1 Visit 3 (t0) (Day 0)

The study participants will return the containers containing the lozenges to a member of the study team. Study participants will then undergo an oral hard and soft tissue exam as well as measurements of probing depth (PD), attachment level (AL), visible plaque index (VPI), gingival index (GI) and bleeding on probing (BOP) and recorded on the Oral Assessment Form (Appendix 7). The biospecimen collection will include gingival crevicular fluid (GCF), plaque, saliva and a saline oral rinse. Additionally, study participants will be asked to refrain from any oral hygiene for 21 days and to continue using the lozenges they were assigned, one during the morning, and one during the evening. Researchers will query participants on their use of NHPs, as well as any adverse effects they experienced.

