# 9.2.2 Reporting Procedures for Serious Adverse Events

Any adverse event that is serious or potentially serious requires additional detailed reports and follow-up. A serious adverse event must be reported via telephone to the sponsor's representative immediately (within 24 hours) so as to facilitate discussion and implementation of necessary follow-up measures, and to enable the sponsor to submit necessary reports to regulatory authorities and other investigators. Following the initial telephone notification, the investigator must complete and submit a Serious Adverse Event Report Form to the sponsor within one calendar day. Serious Adverse Event

Report Forms will be provided to the investigator upon initiation of the study. Once the sponsor reviews the Serious Adverse Event Report Form, additional information may be requested from the investigator to allow appropriate medical evaluation and determine the regulatory reporting requirements.

The investigator is responsible for following all adverse events, especially those deemed "serious", until resolution or until the event is no longer of clinical concern, and for providing these data to the sponsor in an agreed-upon format. The investigator is also responsible for reporting all serious adverse events to the Institutional Review Board (IRB) overseeing the conduct of the study at the respective study center, according to the rules and procedures established by the IRB.

Safety will be evaluated by oral examinations, clinical laboratory evaluations, descriptive analysis of AEs (including incidence, severity, seriousness, andrelatedness), and immune response, over the entire period of the study.

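### Section 8 plans blood, tissue and subset analyses of neutrophils, but the visit and laboratory sections describe no blood or tissue collection and no subset assay

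*Protocol*

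**What the plan says.** Protocol Section 8.0 contains two neutrophil analyses. The first is a correlation: "Correlations between tissue and blood neutrophil subsets and standard periodontal disease parameters from oral exam will be assessed". The second covers "Oral neutrophil counts as well as neutrophil subset formation during day 0, 7, 14, 21, 28 and 35", and these quantities "in oral rinse samples as well as blood samples will be compared using one-way analysis of variance" with Tukey comparisons. Taken literally, that sentence pairs oral counts with blood samples. I read it as counts and subsets in both rinse and blood.

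The specimens are listed visit by visit. Section 6.5.1 (Visit 1, Day -14) says: "The biospecimens collection will include gingival crevicular fluid (GCF), sub-gingival plaque, saliva and a saline oral rinse". Section 6.6.1 (Visit 3, Day 0) says: "The biospecimen collection will include gingival crevicular fluid (GCF), plaque, saliva and a saline oral rinse". The other six visit sections name the same four specimens.

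The laboratory work is in Sections 7.5 to 7.7. For the rinse, Section 7.7 says: "The oral rinse samples will undergo oral neutrophil count". Section 7.5 also lists an oral neutrophil count on GCF, next to a chemokine panel and targeted proteomics. Section 3 names the oral neutrophil phenotype among the things the study evaluates.

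**The concern.** An analysis needs a specimen and an assay. The opening sentence of the statistics section rests on two specimen types, blood and tissue, and on a subset assay, and the operational sections provide none of them. A statistical analysis plan can refine a model, but it cannot supply samples that the protocol does not collect.

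If the text stays as it is, two stated analyses will return nothing, and the final report will have to explain why. The phenotype interest in Section 3 would be served only by a count, which does not measure phenotype. The neutrophil measure that does have data, the rinse count, is tied to a one-way analysis of variance across days that names no treatment arm.

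**Working it through.** No figure is at issue, so the check is a cross-reference of what Section 8 needs against what Sections 6 and 7 provide.

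Inputs: the quantities named in Section 8.0, the specimen lists in Sections 6.5.1 to 6.7.3 (eight visits), and the assays in Sections 7.5 to 7.7.

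| Neutrophil quantity in Section 8 | Specimen in visit text | Assay in Section 7 | Data on the visible text |
|---|---|---|---|
| Tissue subsets | 0 of 8 visits | none | none |
| Blood subsets | 0 of 8 visits | none | none |
| Blood counts | 0 of 8 visits | none | none |
| Oral rinse subsets | 8 of 8 visits | none | specimen but no assay |
| Oral rinse counts | 8 of 8 visits | count (7.7) | yes |

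So 1 of 5 quantities has both a specimen and an assay. Three have neither. One, the rinse subsets, lacks only an assay description. A sixth quantity, the GCF neutrophil count (7.5), has a specimen at 8 of 8 visits and an assay, but the Section 8 comparison does not name it.

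Reading *tissue* loosely as neutrophils recovered from the mouth does not close the gap. It would supply a specimen, but still no subset assay, and it does nothing for blood.

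The remaining text points the same way. The recruitment flyer, where it describes biospecimens, mentions saliva and dental plaque only.

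The analysis attached to the rinse count:

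- The stated method is a one-way analysis of variance over Days 0, 7, 14, 21, 28 and 35 with Tukey comparisons. If day is the factor, there are 6 × 5 / 2 = 15 pairwise contrasts. With two arms as the factor there would be one contrast, and a multiple-comparison step would have no purpose. The text therefore reads as a comparison of days.
- With 60 participants this is 60 × 6 = 360 values from 60 people, and a one-way analysis treats them as independent.
- The explicit two-treatment comparison in Section 8, with possible baseline adjustment, is written for the bleeding scores only.
- The series starts at Day 0. Product is first handed out at Visit 1 (Day -14), so Day 0 comes after 14 days of lozenges and is not a pre-treatment baseline. The rinse is also collected at Day -14, so a pre-product value is available.

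**The case against.** The strongest reply is that the visit lists are not closed. They say what collection will *include*, and they leave out halimetry, although halimetry is objective 5 and has its own Section 7.8. Section 6.7.3 sends the reader to Figure 1 for the procedures at each time point, and that figure is not available here. The health questionnaire (question 16) asks about past problems with a blood sample, which would fit an intended draw. The error could then lie in Sections 6 and 7 (collection omitted) and not in Section 8 (analysis left in).

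Much of this stands. A reader might infer that blood will certainly not be drawn and that these analyses can never be run. The documents do not support that: they show absence from the visible text and do not settle which side is wrong. Nor can anything be said about whether Figure 1 agrees with the visit text. What the reply does not remove is the mismatch itself. Halimetry has a Section 7 entry, while blood, tissue and subset assays have none. Question 16 is a general history item that schedules nothing.

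Three other inferences should also be resisted:

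- A reader might take the rinse count as the only neutrophil measure. Section 7.5 lists a count on GCF as well.
- A reader might extend the point to the safety statement in Section 9.2.2 ("Safety will be evaluated by oral examinations, clinical laboratory evaluations, descriptive analysis of AEs"). That is a separate matter in generic wording, and the chemokine panel in Section 7.5 could supply the immune response that the same sentence mentions.
- A reader might think that the trial's aims are at risk. None of the five objectives in Section 2 mentions neutrophils, blood or tissue.

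Finally, an unseen analysis plan may give the rinse count an arm comparison. That would settle the model, but not the missing specimens and assay.

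**Conclusion.** The inconsistency is real and internal to the protocol. Section 8 plans analyses of tissue and blood neutrophil subsets, blood neutrophil counts and subset formation, and the visible visit and laboratory sections describe neither the specimens nor a subset assay. On that text, 4 of the 5 neutrophil quantities named would have no data. The oral rinse count can be analysed, but the method stated for it has no arm term.

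Severity is minor. The neutrophil interest appears in the Section 3 overview and in Section 8, not in the listed objectives, so the microbiome, clinical, onset and resolution, colonisation and halitosis aims keep their data.

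The conclusion assumes that Figure 1 and the removed pages do not contain a full blood or tissue procedure and a subset assay. If they do, the remedy is to carry that content into Sections 6 and 7.

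**What to change.** Reconcile Section 8 with Sections 6 and 7 in one of two ways.

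1. If the sponsor intends the blood, tissue or subset measures, add the collection, its visits and the assay to Sections 6 and 7 and to the consent. This costs new samples and laboratory work. Under Sections 12.6 and 12.7 it also needs an amendment and prior ethics approval, including approval of the revised consent form.
2. If not, remove the tissue, blood and subset analyses from Section 8 and the word *phenotype* from Section 3. This costs wording only, and the sponsor gives up a claim for which no data are planned.

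In either case, replace the one-way analysis across days for the rinse count with:

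- an arm comparison at Day 21, the end of the no-hygiene phase, adjusted for the Day -14 count: Day 21 count = intercept + arm effect + slope × Day -14 count + error, reporting the arm effect with its 95% confidence interval;
- a correlation of the rinse count with participant-mean BOP and GI at a named visit, so that each participant contributes one pair of values.

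Both use a specimen already listed at every visit, so this part needs no extra sample.

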The classical model of experimental gingivitis (EG) was developed in 1965 by Loe and Silness who convincingly demonstrated the causative relationship between the accumulation of dental plaque and the development of clinically evident gingivitis in healthy young adults abstaining from all oral hygiene practices for a 21-day period. Furthermore, on resuming customary oral hygiene practices, all study participants demonstrated a return to gingival health within two weeks (Loe et al., 1965). To understand how the participants of this study returned so quickly to gingival health we can reflect on our current understanding that our clinically healthy state is an active and dynamic process.

Neutrophils, a type of white blood cell (leukocyte), represent a key component of the innate defence system that protects periodontal tissue from both gingivitis and periodontitis. Not only are they the first line of cellular defence, but they are among the most abundant leukocytes within the periodontal tissues (Hirschfeld, 2020). For example, gingivitis is associated with a significant increase in the number of neutrophils that migrate to periodontal tissue. In contrast, individuals with too few neutrophils brought about by either congenital deficiencies in neutrophil numbers, or transit (LAD 1 and 2) or have an induced neutropenia by chemical induction with antimitotic agents such as cyclophosamide invariably develop periodontitis. Likewise, studies in KO mice that are defective in neutrophil transit also develop periodontitis. Consistent with the key contribution of neutrophils to both gingivitis and periodontitis, neutrophil transit to gingival tissue is highly regulated. The periodontium contains a highly orchestrated expression of select innate host defense

mediators that facilitate the transit of neutrophils from the highly vascularized gingival tissue to the gingival crevice, where they form a "wall" between the host tissue and the dental plaque biofilm.

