#### 2. STUDY OJECTIVES

- 1) The aim of this study is to evaluate the efficacy of S. salivarius SALI-10 in modulating the oral microbiome and preventing gingivitis, using a placebo-controlled experimental gingivitis model. Specifically, the investigators aim to:

  Microbiome Modulation:
  - Assess the ability of SALI-10 to maintain higher levels of beneficial streptococci (S. sanguinis, S. oralis, S. parasanguinis and SALI-10) during plaque accumulation.
  - Determine whether SALI-10 prevents or delays the increase of gram-negative periopathogens (Tannerella, Prevotella, and Porphyromonas) and dysbiosis.
- 2) To evalute the effects of probiotic Sali-10 intake regarding clinical parameters of periodontal health during an experimental gingivitis.
- 3) To assess differences in the onset of gingivitis, the extent of the condition, and its resolution among experimental and control groups.
- 4) To evaluate the capability to establish or increase oral colonization by *Streptococcus* salivarius SALI-10. The expected outcomes will be attributed to the effect of antimicrobial and immunomodulation metabolites (mainly, the natural product Salivaricin 10) produced by this strain present in the probiotic.
- 5) To analyze the level of sulfured compounds emitted from the oral cavity with a halimeter (Halimeter PLUS) from each study participant to assess the level of halitosis objectively, then evaluate the difference between the control and test groups as they go through the experimental gingivitis clinical trial.

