# 6.7.3 Visit 8 End of Study (t5) (Day 35)

The study participants will return the containers containing the lozenges to a member of the study team. Study participants will then undergo an oral hard and soft tissue exam as well as measurements of probing depth (PD), attachment level (AL), visible plaque index (VPI), gingival index (GI) and bleeding on probing (BOP) and recorded on the Oral Assessment Form (Appendix 7). The biospecimen collection will include gingival crevicular fluid (GCF), plaque, saliva and a saline oral rinse. The study participants will be informed that this is the end of the study. They will be given their compensation and told that they may resume their regular oral hygiene. Once the study has been completed, the manufacturer will reveal to which group was the probiotic assigned to (either A or B). Afterwards, the investigators will inform participants to which group they were assigned and will ask for their feedback in regards to their experience. Researchers will query participants on their use of NHPs, as well as any adverse effects they experienced.

Please refer to figure 1. Illustrating the breakdown and timeline of the study as well as the relevant study procedures at each time point and the objectives.

Figure 1. Study Flow Infographic

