#### 7.5 Gingival Crevicular Fluid (GCF) Samples

Before GCF collection, the plaque index will be recorded. The sites to be sampled will be isolated with cotton rolls and gently air-dried. GCF samples will be collected with sterile paper strips (Periopaper strips, Oraflow Inc.) that will be inserted into the gingival crevice until mild resistance is felt and left in place for 30 seconds. GCF will be collected from the mesiobuccal and mesiopalatal surfaces of teeth (#'s 3, 4, 5, 12, 13, 14). Paper strips visibly contaminated with saliva and blood will be excluded from the study. All samples will be collected in microcentrifuge tubes. They will be transported on ice and stored within 24 hours at -80°C until processing. At our lab at Dental Sciences building, at University of Toronto, Faculty of Dentistry, these samples will undergo 40-plex chemokine analysis, oral neutrophil count and targeted proteomics

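### The one-way ANOVA with Tukey over Days 0 to 35 names no arm and no participant term, so most outcomes have no clear test of SALI-10 against placebo

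*Protocol*

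**What the plan says.** Section 8.0 contains three relevant pieces.

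- **Clinical parameters.** Changes in bleeding on probing, gingival index, plaque index and probing depth "during day 0, 7, 14, 21, 28 and 35 will be compared using one-way analysis of variance (ANOVA) followed by Tukey multiple comparison".
- **Neutrophils.** Counts and subsets on the same six days "in oral rinse samples as well as blood samples will be compared using one-way analysis of variance (ANOVA) followed by Tukey multiple comparison". The section also opens with correlations that involve tissue and blood neutrophil subsets.
- **Bleeding index.** Scores are averaged per participant at baseline and at a 3-week exam. ANOVA, possibly ANCOVA with the baseline score, "will be used to compare the difference between the two test treatments using the 95% confidence level".

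Only the third piece mentions treatment. None mentions a participant effect or an arm-by-day term.

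Objective 3 in Section 2 is "To assess differences in the onset of gingivitis, the extent of the condition, and its resolution among experimental and control groups". Objective 2 asks for the effect of SALI-10 on the clinical parameters. Section 6.1 defines two randomized groups.

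**The concern.** The objectives call for comparisons between arms, but the method named for most outcomes does not mention arms. If day is the factor, a significant result shows that gingival measures worsen when brushing stops and recover when it resumes. Section 1 says of the classical model that it produced "the development of clinically evident gingivitis in healthy young adults abstaining from all oral hygiene practices for a 21-day period". That result is expected in both arms whether or not SALI-10 works, so it is not evidence of efficacy.

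Apart from bleeding at one 3-week exam, no clinical or neutrophil outcome has a stated test of SALI-10 against placebo. The same holds for the course of onset and for resolution on Days 28 and 35.

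The method also ignores that every participant contributes all six values.

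A separate inconsistency: Section 8.0 analyses blood and tissue neutrophils, but the visit texts list neither blood nor tissue.

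**Working it through.** **Inputs.** From the protocol: 60 participants (Section 4.2), two arms (Section 6.1), six analysis days and a 0.05 level (Section 8.0, where the level is given for the bleeding test). Assumed: 30 per arm, two-sided tests, SD 1 at every visit, and exchangeable within-person correlation ρ = 0.3 / 0.5 / 0.7. The protocol gives no correlation, SD, effect size or power, so it has no figure to reproduce.

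**1. Which factor is meant?** With two groups of 30, the Tukey critical value is 2.0017, identical to Student's t on 58 df. Tukey would be redundant for an arm comparison at one day. With six days it covers 6 × 5 / 2 = 15 pairs, all of them day against day and none SALI-10 against placebo.

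**2. Degrees of freedom.** One-way by day: 5 and 360 − 6 = 354. With participant as a block: 5 and 59 × 5 = 295.

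**3. Standard error of a change between two days.**
- One-way ANOVA: √(2/60) = 0.183.
- Correct: √(2(1 − ρ)/60) = 0.153 / 0.129 / 0.100.
- Ratio 1/√(1 − ρ) = 1.20 / 1.41 / 1.83.

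**4. Type I error of the day test.** The critical F is 2.24. With no day effect, the between-day mean square has expectation 1 − ρ while the error mean square stays at 1. A quick approximation is therefore the tail of F(5, 354) beyond 2.24/(1 − ρ) = 3.20 / 4.48 / 7.46, which gives 0.8% / 0.06% / 0.0001%. Simulation (100,000 trials per correlation):

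| Test, no effect present | ρ = 0.3 | ρ = 0.5 | ρ = 0.7 |
|---|---|---|---|
| One-way F by day | 0.86% | 0.07% | 0.00% |
| Tukey, any of 15 day pairs | 0.97% | 0.10% | 0.00% |
| Participant as a block | 5.0% | 5.0% | 5.0% |

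**5. What the day test detects when SALI-10 does nothing.** Both arms follow the same assumed profile on Days 0 to 35: 0, 1/3, 2/3, 1, 1/2 and 0 times a peak (20,000 trials).

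| Proportion significant | ρ = 0.3 | ρ = 0.5 | ρ = 0.7 |
|---|---|---|---|
| Peak 1.0 SD, one-way F | 100% | 100% | 100% |
| Peak 0.5 SD, one-way F | 71% | 68% | 64% |
| Peak 0.5 SD, participant as a block | 89% | 97% | 99.9% |

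**6. Other readings of the same sentence.**
- Arms compared at each single day: type I error 4.9% to 5.1% per visit, which is valid.
- Arms compared with all visits pooled as independent: 22% / 29% / 36% (4,000 trials), badly inflated.
- Twelve arm-by-day cells: 12 × 11 / 2 = 66 Tukey pairs, of which 6 compare the arms on the same day. Each of those has a type I error of about 0.1%.

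**7. Blood and tissue.** Each visit lists the same specimens; at Visit 8, for example, "The biospecimen collection will include gingival crevicular fluid (GCF), plaque, saliva and a saline oral rinse". For neutrophils, Section 7.7 says "The oral rinse samples will undergo oral neutrophil count", and Section 7.5 says of GCF that "these samples will undergo 40-plex chemokine analysis, oral neutrophil count and targeted proteomics". Neither the visit texts nor Section 7 describes a blood draw or tissue sample.

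**The case against.** The strongest reply is that the text never says day is the factor. Two of the readings in step 6 do compare arms: by single day, which is valid, and by twelve cells, which is very conservative but not anti-conservative. That is fair, and the consequences above depend on the reading. But no reading is written down, and the candidates range from a valid arm test through a test of time to an arm test with 22% to 36% false positives.

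A second reply is that the statistical analysis plan may settle this. The protocol does not leave the method open, however. It names one, and a plan that used a mixed model would contradict it.

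Third, the type I figures depend on the assumed covariance. With first-order autoregressive correlation and the same adjacent-visit values, the day test rejects in about 3.3% / 2.1% / 0.8% of null trials, and unequal spread over visits moves the figures again. This stands: the size is uncertain. The direction was conservative in each case checked, so ignoring the correlation on the day reading costs power and does not create false claims. The main defect is that the test addresses the wrong question.

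Fourth, a day comparison is a legitimate check that induction worked, and the bleeding test between arms is reasonable. Both are true, but neither supplies the missing arm comparisons.

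On blood, the visit lists may not be exhaustive: they also omit the halimeter reading. Figure 1 is not shown. The point is therefore a request to reconcile, not proof that no blood is taken.

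**Conclusion.** The concern holds and should be fixed before unblinding. It is certain that Section 8.0 prescribes a one-way ANOVA with Tukey over six repeated days without an arm or participant term, and that its only stated arm test covers mean bleeding at baseline and 3 weeks. Gingival index, plaque index, probing depth, neutrophils, the onset course and the resolution phase are left without one.

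That day is the factor is an inference, well supported by the six listed days and the use of Tukey. On that reading the test would be significant almost always given a 1 SD rise common to both arms, and its error rate falls well below 5% under the assumed exchangeable correlation. The correlations, peaks and equal allocation are assumptions.

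**What to change.** In Section 8.0, replace the one-way ANOVA with a mixed model for repeated measures on per-participant visit means.

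- **Terms:** arm, visit, arm-by-visit and the Day -14 value, with a within-participant covariance whose structure can be left to the statistical analysis plan. Day -14 is the pre-product value, since lozenges are dispensed at that visit (Section 6.5.1) and Day 0 is already on product. Day -14 also precedes the first cleaning, so state whether Day 0 enters as an outcome visit.
- **Contrasts:** name one lead arm contrast per outcome, for example Day 21, the end of induction. Treat Days 7 and 14 (onset) and Days 28 and 35 (resolution) as supportive, or adjust for multiplicity. Five unadjusted contrasts carry a 21% / 18% / 15% chance of at least one false positive per outcome at ρ = 0.3 / 0.5 / 0.7.
- **Cohabitants:** Section 6.1 places them in the same arm, so say how any such pairs will be handled.
- **Change over days:** if it is still wanted, label it as a check of the induction model.

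Separately, reconcile the blood and tissue neutrophil analyses with the visit schedule, and confine neutrophil analyses to samples actually collected.

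The cost of the model change is rewording: it needs no new data and runs in standard software. The blood and tissue point needs a correction either to the analysis text or to the schedule.
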